on positive pressure support for at least 7 days after birth AND/OR on any other respiratory device such as nasal cannula with flow rates greater than 2LPM receiving supplemental oxygen of greater than 21% for at least 7 days after birth. Positive pressure for the purposes of this study is defined a nasal cannula delivering a flow of 2 LPM or higher, continuous positive airway pressure (CPAP), non-invasive positive pressure ventilation or non-invasive mechanical ventilation (NIPPV/NIMV), as well infants who are intubated or have a tracheostomy for oxygenation and ventilation related to their lung disease, irrespective of the mode of ventilation. We will exclude infants who were previously on room air without a respiratory device who were intubated for the purposes of surgery and were not receiving respiratory support as defined above prior, those intubated for other airway issues such as tracheal stenosis, broncho- or tracheomalacia, etc and not for the management of BPD. Additional patients to be excluded include those with suspected or proven genetic or other major congenital anomalies that may impact cardiac and lung function including cardiac and lung anomalies, as well as those at the time of enrollment who require surgeries that will impact their ability to be placed in prone positioning (eg gastroschisis, omphalocele, etc).

Patients meeting the aforementioned criteria will be assigned to 1. usual care in which positioning and duration in each position is random per usual nursing routine OR 2. Receive standardized scheduled daily prone positioning starting on day of life 7. As part of normal developmental care, most infants are evaluated and have care rendered (touch-time), if stable, and repositioned at set three-hour intervals to permit uninterrupted sleep and/or rest. The hands-off interval will be maintained throughout the study interval. Infants randomized to the standardized scheduled daily prone positioning will be placed in prone body position for a total of 6 hours daily, that is prone position for 3 hours, followed

by supine positioning for 3 hrs, then placed in prone position for another 3-hour interval. Standardized daily positioning will occur for randomized patients until 36 weeks or discharge whichever is first. If needed, position aids, which are part of the normal care routine in our ICU, may be used to facilitate maintenance of prone or supine positioning.

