Identification: Each day, NICU admissions will be reviewed via the electronic medical record and infants who are born with a birthweight of less than 1500 grams will be identified. On day of life (DOL) 5-7, of those infants identified, those parents of infants who are still maintained on positive pressure ventilation and or >21% FiO₂, will be approached and consented for inclusion in the study.

Consent: Families will be approached in person in the Neonatal Intensive Care Unit or Post-Partum Unit between DOL 5-7 and consent obtained for participation in the study by [name] or [name]. One parental signature will be required. Written study material and copies of consent forms will be provided for families to keep. There will be no cost to the patient and no remuneration offered. Families may withdraw consent at any point of the study. See separate consent form, appendix 1.

Procedures: Consent will be obtained between DOL 5-7. Subjects will undergo block randomization. Once randomized, those patients who are assigned to standardized, scheduled prone positioning, will be placed in prone position, with the head turned either right or left per nursing or patient desire, for a total of 6 hours daily, during daytime hours, if clinically stable. They will be placed in prone position for 3 hours, followed by supine positioning for 3 hours, then placed in prone position for another 3-hour interval. If needed, position aids, which are part of the normal care routine in our ICU may be used to facilitate maintenance of prone or supine positioning. If an infant is felt to be too unstable, or significantly

intolerant of prone positioning, they may be positioned per nursing or patient comfort. If infant was already in the prone position per nursing routine prior to the start of prone positioning per study protocol, we will await change to a different position before initiating study protocol for infants assigned to scheduled prone positioning. This is to avoid infants being placed in prone position for > 3 consecutive hours at a time). Alternating between supine and position allows us to detect any short term immediate changes in oxygenation and vital signs attributable to a change in positioning between prone and supine.the two positions.

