Both infants randomized to standardized prone positioning and usual positioning will have a bedside card card identifying that the infant is a study participant and will serve as a way to document the number of times any infant enrolled in the study is placed in prone positioning even if not randomized to standardized prone positioning. The bedside card also facilitates the infantâ€™s nurse being aware of the time of day for prone into supine position change for those who are randomized to prone positioning. On the weekly anniversary of the infantâ€™s first placement in prone position for the study, physiologic and clinical data will be retrieved.

Risk/Benefit: anticipated medical, social, psychological, and/or legal risks are minimal; however uncommon risks to be being placed prone may include movement or dislodgement of a breathing tube or of an intravenous (IV) catheter. These uncommon risks will be minimized by staff paying strict attention to the positions of these devices during movement from prone to supine position and vice versa. Additionally, documentation of the positions of these devices is routine and will permit tracking of change in position of the devices. Potential benefits include a decrease in the severity and occurrence of moderate to severe BPD, a common condition of the lung related to premature birth.

Data storage and maintenance of confidentiality: Data will be reviewed and retrieved from the electronic medical record into a computerized study data form kept on a password protected computer in a locked office. Only the 2 study personnel, [name] and [name] will access study files to check or edit data. Consent forms will also be kept in a locked office. The study database will be permanently deleted and paper data collection tools will be shredded. Subjects will not be video or audiotaped during this study.

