Personnel: Neonatologists [name] and [name] will be responsible for consenting families and determining randomization assignment. Bedside nurses along with respiratory therapists will be responsible for position changes and documentation of physiologic metrics and vital signs as part of the normal ICU care practice. [name] will collect study data for analysis. Nurse practitioner [name], BSN, DNP, will be responsible for assigning the primary outcome of moderate or severe BPD, at or after 36 weeks post conceptional age. She will be provided a list of study participants identified only by study number at 36 weeks post conceptional age, their respiratory support parameters and will assign the primary outcome of moderate (Grade 2) or severe (Grade 3) BPD.

Randomization: Block randomization with variable block sizes will be performed in order to ensure equal sample sizes over time. The treatment (standardized prone positioning) ratio to control (usual positioning) ratio will be 1:1. The randomization list will be generated by the study statistician and will be maintained under locked conditions. Blinding of staff is inherently not feasible as scheduled prone position changes are obvious to caretakers.

Evaluations and measures: Incidence and severity of BPD will be assessed at 36 weeks post conceptional age. As part of usual NICU care, infants, especially those on respiratory support have vital signs and other physiologic parameters recorded routinely every 3 hours,

but this may occur as frequently as every hour in the sickest infants. Enrolled infants will have physiologic data and vital signs evaluated and recorded at start of hands-on time, at the 1 hour mark after scheduled position change to prone, at the time of switch to supine, 1 hour after 2nd switch to prone position, and at the time of conclusion of study positional changes. For infants randomized to usual care, we will record similar data from a period of 3 hands-on intervals (total of 9 hours).

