We aim to record and collect the following data once weekly on the weekly anniversary of the infantâ€™s first study prone positioning and the date of randomization onto the study for those study participants who were randomized to usual care: transcutaneous CO₂ (TCO₂) if available or PCO₂ from any blood gas, SaO₂ from cardiopulmonary monitors, PaO₂ from arterial blood gases within 1 hour of positional change (if available), ventilator or other respiratory support modality settings and direction of changes within 1 hour of positional change. Specifically, percent change in inspired oxygen, change in ventilator rate (breaths per minute), tidal volume (milliliters), peak inspiratory pressure (cm H₂O), positive end expiratory pressure (cm H₂O) and the number of episodes of oxygen desaturations will be collected. Current comorbidities, most recent chest x-ray findings within a 7day interval will also be documented once weekly.

Other data: duration of time on any respiratory support (days), duration of use of endotracheal tube, non-invasive positive pressure ventilation (NIPPV) and continuous positive airway pressure (CPAP), time to FiO₂ of 21% (irrespective of type of respiratory interface), type of medications to treat BPD (use of oral, inhaled or intravenous postnatal steroids for mitigation of BPD, caffeine, diuretics daily or intermittent), presence of pulmonary hypertension as documented by echocardiogram, use of sedatives and analgesics, pharmacologic treatment of

GERD, use of inhaled nitric oxide on DOL 7 or later. Additionally, the mode of ventilation at 7 days after birth, DOL when maximal feeds achieved (total fluids of 160 milliliters per kilogram per day), DOL at which feeding by mouth was initiated and DOL at which feeds were administered by mouth only, diagnosis of plagiocephaly, and the duration of NICU stay. Demographic data of interest include gestational age at birth (weeks), maternal comorbidities, infant comorbidities, growth status (small, appropriate or large for gestational age), weight at birth (kilograms) and use of antenatal steroids.

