Weekly physiologic and ventilatory data will be collected until the infant reaches 36 weeks postconceptional age or discharge from the NICU, or is on 21% FiO₂, i.e. O_2 room air, without any respiratory interface, whichever is earlier. For the purposes of our study, the primary outcome of moderate (Grade 2) to severe (Grade 3) BPD will be clinically defined and assigned at 36 weeks PCA based on the 2019 study by the Eunice Kennedy Shriver National Institute of Child Health and Human Development Neonatal Research Network which assessed the definition of BPD that best predicted early childhood morbidity.⁽¹¹⁾ The definitions are as follows:

Severe (Grade 3) BPD: If an infant requires invasive positive pressure ventilation via an endotracheal or tracheostomy irrespective of the amount of FiO₂.

Moderate (Grade 2) BPD: If an infant requires nCPAP, NIPPV, HFNC, or NC > 2 liters per minute flow and receiving $\geq 21\%$ FiO₂.

Infants receiving NC 2 liters per minute or lower flow rates, irrespective of the FiO₂ received, will be considered as having mild (Grade 1) BPD and will not be assigned the primary outcome.

Statistical Considerations: Demographic and clinical variables assessed at baseline will initially be summarized by intervention arm using standard descriptive statistics to confirm

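### Weekly data stop at room air while positioning continues, so later weekly comparisons of FiO2, support level, saturation and desaturation cover only infants still on support

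*Combined protocol and SAP*

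**What the plan says.** **End of positioning (Study plan).** "Standardized daily positioning will occur for randomized patients until 36 weeks or discharge whichever is first". Reaching room air does not end it.

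**End of weekly data (Evaluations and measures).** Weekly physiologic and ventilatory data run to 36 weeks post-conceptional age (PCA), NICU discharge, or 21% oxygen in "room air, without any respiratory interface, whichever is earlier". An infant on 21% with an interface is still collected. The text does not say whether the first room-air visit is itself recorded. The weekly items include monitor saturation, support settings and inspired oxygen, and "the number of episodes of oxygen desaturations will be collected".

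**Start of weekly data.** Evaluations and measures dates the weekly anniversary from the infant's "first study prone positioning and the date of randomization onto the study for those study participants who were randomized to usual care". The bedside-card paragraph that follows Procedures names only one event: at the weekly anniversary of the "first placement in prone position for the study, physiologic and clinical data will be retrieved". Prone placement is scheduled "for a total of 6 hours daily, during daytime hours, if clinically stable", and if an infant is too unstable or "intolerant of prone positioning, they may be positioned per nursing or patient comfort".

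**Analysis (Statistical Considerations).** Continuous variables at a given visit are compared by two-sample t-test, and weekly data by generalized linear mixed models. Missing data are handled by available-data analysis and by chained-equation imputation. All analyses are intent-to-treat and exploratory. The stated goal of the pilot is preliminary effect sizes.

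**The concern.** Coming off all support is a post-randomisation response, and one that prone positioning is hoped to bring forward. A rule that ends measurement at that moment removes infants because they improved. If more prone infants improve, more are removed from the prone arm, and those left are on average the sicker ones. A later weekly comparison then asks how the infants still on support differ, not how the randomised groups differ.

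For FiO2 and support level the removed values are known: 21% and none, unless support resumes. The plan does not say to use them, and imputation would replace them with modelled values. For saturation and desaturation, nothing after room air enters the weekly dataset.

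At stake are the exploratory weekly effect sizes, which might inform a later trial. The primary outcome is not at stake.

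The start rule is a separate and smaller matter. A prone-arm infant who is placed late or never has a delayed or absent week 0, while an equally unstable usual-care infant is collected from randomisation. That does not fit the intent-to-treat statement.

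**Working it through.** Differences are prone minus usual care, in FiO2 percentage points.

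**1. The plan's own figure.** At 31% versus 21% with 30 per arm, the half-width is 1.96 × √(0.31×0.69/30 + 0.21×0.79/30) = 22.05 points, against a stated 22. It reproduces. It concerns BPD at 36 weeks, which is assigned whether or not weekly data have stopped, so it is unaffected.

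**2. Week 4 by hand.** Assumed inputs: 6 of 30 usual-care and 9 of 30 prone infants in room air; mean FiO2 30% on support.
- All infants: (6×21 + 24×30)/30 = 28.2 and (9×21 + 21×30)/30 = 27.3; difference **-0.9**.
- Still collected: 30 and 30; difference **0.0**.
- If the 3 extra weaned infants are mild and would otherwise have needed 23%, the 21 prone infants left average (24×30 - 3×23)/21 = 31.0. The difference is **+1.0** among those collected, but (9×21 + 651)/30 - 28.2 = 28.0 - 28.2 = **-0.2** in all infants.

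**3. Simulation, benefit only through earlier weaning.** All inputs are assumed.
- Births at 23–31 weeks. Week k from day of life 7 falls at PCA = gestational age + 1 + k, so week 4 is within 36 weeks for births up to 31 weeks.
- 10%, 20% or 40% of usual-care infants in room air without an interface by week 4, and 10 points more in the prone arm.
- Baseline FiO2 averaging about 32 (SD about 6), falling 0.5 a week, floor 21. The chance of weaning depends on baseline FiO2 to three degrees (g = 0, 0.1, 0.2).
- The mixed model has a random intercept, week effects and arm. The plan does not specify its terms.

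| Analysis | All infants | First room-air visit not recorded | Recorded |
|---|---|---|---|
| Week 4, available data | -0.49 to -0.93 | +0.07 to +0.71 | -0.37 to +0.27 |
| Week 4, imputed | – | 0.00 to +0.08 | -0.32 to -0.70 |
| Mixed model, week 1 to 36 weeks PCA | -0.46 to -0.86 | +0.01 to +0.30 | -0.34 to -0.68 |

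A repeat run at g = 0.1 agreed: week 4, -0.66 to -0.83, then +0.32 to +0.55, then about 0; mixed model, -0.65 to -0.76, then +0.07 to +0.14, then -0.45 to -0.63.

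**4. Benefit as a uniform FiO2 reduction.** The full mixed-model effect is -0.51 to -1.02, and the stop rule moves it by up to about 0.2 points in either direction. In the case with 40% of usual-care infants off support, a repeat run gave -0.50 in full and -0.59 or -0.68 under the two readings of the stop rule, so the benefit looked larger. At week 4 the full effect is -0.68 to -1.05, and the stop rule makes it 0.04 to 0.28 points smaller.

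**5. Sampling error.** The 95% half-width at 30 per arm is 2.9 to 3.2 points for the mixed model and 3.3 to 4.2 at week 4. Every shift in steps 2 to 4 is smaller.

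**6. Saturation and desaturation.** Under the weaning assumptions, 6–39% of weekly visits up to 36 weeks PCA in usual care, and 12–47% in the prone arm, would have no record. The direction of any bias was not computed.

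**7. Start rule.** Consent is at day of life 5–7 and positioning starts on day 7. The randomisation day is not given; if it falls on days 5–7, the planned offset is 0 to 2 days. If the sickest 1, 2 or 3 of 30 prone infants had no weekly data, the prone mean would shift by -φ(z)/(1-f), where f = 1/30, 2/30 or 3/30 and z cuts off the upper fraction f. That gives at most -0.08, -0.14 or -0.20 SD, and half that if severity and outcome correlate at 0.5. The documents give no frequency for such infants.

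**The case against.** The case for leaving the rule alone has weight.

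- *Ventilator settings have no meaning once there is no interface, and the short-term response to a position change is a main use of these data.* This stands. Settings and responses that exist only on support are not affected.
- *Earlier weaning is captured elsewhere.* This stands too. Days on support, time to FiO2 21% and 36-week BPD do not depend on the stop rule. The first two could be used to fill in later FiO2 and support level, but the plan does not say so, and they recover no saturation or desaturation data.
- *Mixed models and imputation deal with it.* Only in part. With earlier weaning as the benefit, the estimate keeps its sign in these models when the first room-air visit is recorded, and the effect is largely lost when it is not. The plan leaves that open.
- *Every weaning input is assumed, and the shifts are below sampling error in an exploratory pilot.* This stands, and it keeps the severity low.
- *Counting from randomisation could put week 0 on a day without study positioning.* This stands if randomisation precedes day 7; the fix allows for it.

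A reader might infer from the two start events that they also cause the restriction to infants on support, or that the arms run on materially different clocks. The documents support neither. The restriction comes from the stop rule alone, and the planned offset is small and may be zero.

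**Conclusion.** The point holds, at low severity. The stop rule conditions later visit-specific and available-data comparisons of FiO2, support level, saturation and desaturation on still needing support. If the benefit is earlier weaning, a week-4 FiO2 comparison can shrink to zero or reverse. A mixed model largely loses the effect if the first room-air visit is not recorded, and keeps a smaller effect of the same sign if it is. These sizes rest on assumed weaning and FiO2 inputs.

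Two stronger readings do not hold. A reader might infer that the rule always hides a benefit; under a uniform FiO2 reduction the mixed-model estimate can move either way, by up to about 0.2 points on a full effect of 0.5 to 1.0. A reader might also infer that the trial's main result is biased; the 36-week BPD outcome and its stated precision are not touched.

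The start rule is a minor, separate wording fault. It matters only for prone-arm infants placed late or never.

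**What to change.** **Evaluations and measures, stop rule.** Continue weekly extraction from routine charts to 36 weeks PCA or discharge in both arms. After room air, record FiO2 21% and support none (actual values if support resumes), with the charted saturations and desaturations. At the least, state that the first room-air visit is recorded and that the known 21% and none are carried forward, not imputed.

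**Statistical Considerations.** Analyse ventilator settings and position-change responses as conditional on being on support, and label them so.

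**Bedside-card paragraph and weekly-data paragraph.** Count weeks from randomisation for every randomised infant in both arms, whether or not prone positioning was started. Position-change readings are taken only on days when study positioning takes place.

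**Cost.** Protocol wording and some extra chart abstraction. No new procedure is needed, since the plan says that "infants, especially those on respiratory support have vital signs and other physiologic parameters recorded routinely every 3 hours". Saturations may be charted less often on room air, so those weeks may be thinner. Positioning and the primary outcome do not change.

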that patient characteristics are distributed similarly across groups. The difference between the intervention and control arms in the rate of BPD at 36 weeks post-conceptional age and other outcomes will be estimated, along with corresponding 95% confidence intervals. In exploratory analyses, the chi-square test will also be applied to assess whether the rates of BPD and other binary outcomes are significantly different between groups, and the two-sample t-test will be used compare the mean values of continuous variables measured at a specific visit. Logistic and linear regression models will also be fit to the data to adjust for any baseline characteristics that are not balanced across groups despite randomization. Weekly physiologic, ventilator and other clinical data will be obtained and analyzed using generalized linear mixed models, with the logit link for binary outcomes and the identity link for continuous outcomes, to account for the correlation in repeated measures from the same infant. Missing data will be handled by analyzing the available data as well as by multiple imputation using chained equations. All analyses will be based on the intent-to-treat approach, and results will be viewed as exploratory and hypothesis generating.

We plan to randomize a total of 60 patients 1:1 to intervention and control (N=30 per arm). Since this is a pilot trial, the goal is to obtain preliminary data on effect sizes. Therefore, formal power calculations were not performed. With 30 patients per arm, the precision, as measured by the width of the 95%CI, with which the true intervention effect (i.e., difference between groups) can be estimated is +/- 25% or better. For example, to gauge the magnitude of the primary outcome of BPD incidence and the potential benefit of standardized prone positioning, we evaluated 2019 BPD rates in our NICU. There were 107 patients described as VLBW at birth. Of those, 34 infants developed moderate to severe BPD, a rate of 31%. If the observed BPD rate is reduced to 21% in the intervention arm for a between group difference of

10%, then the corresponding width of the 95% CI for the true difference will be +/- 22%. We anticipate performing this pilot study over 2-3 years to account for yearly variations in the admission of VLBW patients.

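### The change in FiO2 is listed as an undefined percent change with no planned adjustment for starting FiO2; recording and modelling the FiO2 level would be clearer and at no extra cost (minor).

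*Combined protocol and SAP*

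**What the plan says.** The weekly data list under Evaluations and measures names "percent change in inspired oxygen", alongside ventilator rate, tidal volume and pressures, each given with its own unit. No formula or reference reading is stated. The preceding sentence also collects "ventilator or other respiratory support modality settings and direction of changes within 1 hour of positional change", and the other-data list includes time to an FiO2 of 21%.

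Readings in the prone arm are taken at the start of hands-on time, "at the 1 hour mark after scheduled position change to prone", and at later points in the cycle. For the control arm the text says "For infants randomized to usual care, we will record similar data from a period of 3 hands-on intervals", nine hours in all, with no defined turn. Procedures explains that alternating prone and supine "allows us to detect any short term immediate changes in oxygenation and vital signs".

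On entry, Study plan admits infants "on positive pressure support for at least 7 days after birth AND/OR on any other respiratory device". The oxygen condition above 21% is attached to the second route only. Positive pressure "is defined a nasal cannula delivering a flow of 2 LPM or higher", or is CPAP, non-invasive or invasive ventilation, and that definition has no oxygen requirement. Weekly collection stops early for an infant at 21% only once there is also no respiratory interface.

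Statistical Considerations plans two-sample t-tests at a visit, mixed models with an identity link for weekly continuous data, and regression adjustment for baseline characteristics found to differ between arms. Starting FiO2 is not named. No power calculation was made, and all results are exploratory.

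**The concern.** A relative change in FiO2 behaves awkwardly in this population. The same absolute step takes a different value at each starting level. Rises count for more than the equal falls that reverse them. An infant on CPAP at 21% can enrol, stays in weekly collection, and can only go up from there. The pilot's stated aim is preliminary effect sizes, and an effect size in relative percent depends on the mix of starting FiO2 in the sample, so it carries over poorly to a later trial.

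Not adjusting for the starting value also leaves avoidable noise in a comparison with 30 infants per arm. The missing definition is a problem in itself: two analysts could compute different quantities from the same readings, and in the usual-care arm it is unclear what the change is measured from.

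**Working it through.** **1. The plan's own figure.** The plan gives no SD, effect or power for FiO2. Its only precision figure is for BPD incidence: "We plan to randomize a total of 60 patients 1:1 to intervention and control (N=30 per arm"), 31% against 21%. The half-width is 1.96 × √(0.31×0.69/30 + 0.21×0.79/30) = 22.1%, against a stated 22%. The worst case, 50% in both arms, is 1.96 × √(0.50/30) = 25.3%, against a stated 25%. Both reproduce after rounding. Only the 30 per arm carries over to FiO2.

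**2. Arithmetic of a relative change**, 100 × (after − before)/before:
- Dependence on the start: a 5-point fall from 26% is −5/26 = −19.2%; from 60% it is −5/60 = −8.3%.
- Asymmetry: 25 to 30 is +20%, and 30 to 25 is −16.7%. The mean is +1.7% with no net change. In the extreme, 21 to 42 is +100% and 42 to 21 is −50%, a mean of +25%.
- Floor: a start at 21% allows only zero or a rise.

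**3. Size when nothing changes.** Simulation with 30 per arm and FiO2 floored at 21%. Assumed, not in the documents: 20-40% of infants at room air, the rest with median FiO2 32% and lognormal need, and reading noise SD 1 to 5 points. The correlation between readings was then 0.77 to 0.99. Mean percent change in an arm was about +0.1% at SD 1, +0.3 to +0.4% at SD 2, below +1% at SD 3 and about +2% at SD 5. The rise has the same expectation in both arms. The between-arm false-positive rate stayed near 5% (4.0% to 5.7% in a wider set of scenarios). In that wider set mean absolute change was about zero.

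**4. Power.** A t-test on percent change was compared with regression of the later FiO2 on arm and starting FiO2. With oxygen need above room air cut by 25%, one set of runs gave:

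| At room air | Noise SD | Percent change | Adjusted FiO2 | Relative loss |
|---|---|---|---|---|
| 20% | 3 | 50% | 73% | 1 − 50/73 = 32% |
| 20% | 5 | 25% | 37% | 1 − 25/37 = 32% |
| 40% | 3 | 36% | 54% | 1 − 36/54 = 33% |
| 40% | 5 | 18% | 27% | 1 − 18/27 = 33% |

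Other runs of the same design, varying the assumed spread of oxygen need, gave losses of 17-27%, 22-33% and 24-35% at SD 3-5. The loss was 12-21% at SD 2 and at most 4% at SD 1. With a fixed 3-point effect the gap was small, from essentially none to 5-10% in relative terms.

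**5. A different assumed shape.** Here FiO2 need was normal or lognormal and clipped at 21%, with the effect set so that the adjusted analysis had about 80% power. The result for percent change ran from a 5% gain to a 25% loss at correlation 0.7, and from an 11% gain to a 19% loss at 0.9. A loss of a third appeared only at correlation 0.3 or lower.

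**6. Scale or missing covariate?** Normal theory, comparing a plain change score (SD √(2(1−ρ))) with 80% power for the adjusted analysis (SD √(1−ρ²)), gives 62%, 68%, 73% and 78% at ρ = 0.3, 0.5, 0.7 and 0.9. Part of the loss is therefore due to non-adjustment on any scale. Adjusting percent change for starting FiO2 recovered much or all of the loss in most step 5 scenarios. In further runs of the step 4 design it recovered less than half. The covariate matters throughout, and the scale matters in some settings.

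**The case against.** The strongest reply is that the phrase may not mean a ratio at all. Every other setting in the list carries its own unit, and the unit of FiO2 is percent, so percentage points is a fair reading. The asymmetry and the dependence on starting level then disappear. This stands, and what remains is the undefined reference reading and the missing covariate.

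Second, the phrase sits in a data-collection list. Support settings and time to 21% are collected too, so FiO2 levels may well be available, and Statistical Considerations does not name percent change as the analysed variable. This also stands: it would be wrong to say oxygen need is captured only as a percent change. Equally, no analysis of the level is specified.

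Third, the measure is one secondary item in an exploratory pilot with no planned power. That limits the importance of the point without removing it.

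A reader might go further and infer that the choice costs a third of the power. The documents do not support that: they give no FiO2 distribution, reading noise or effect. A third is near the top of the simulated range and needs both a proportional effect and noisy readings, or weak correlation between readings, which is hard to square with readings about an hour apart in one infant. A reader might also infer that the spurious rise biases the trial's comparison. It does not: under no effect it is common to both arms, and the plan specifies no within-arm before/after test.

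**Conclusion.** The point holds as a minor one. The FiO2 change measure is undefined as to scale and reference reading, and starting FiO2 is not a planned covariate. If the change is relative, it depends on the starting level, cannot fall from 21%, and drifts upward by about 0.1% to 2% when nothing changes. The drift affects descriptive before/after summaries within infants; the randomised comparison and its false-positive rate are unaffected.

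The power cost relative to baseline-adjusted FiO2 ranges from about none (fixed-point effect or low reading noise) to roughly 20-33% (effect proportional to oxygen need, noise SD 3-5). That range rests on the assumed room-air share, spread of need and noise given above. The primary outcome, BPD grade at 36 weeks, is not touched.

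**What to change.** - Evaluations and measures: record the actual FiO2 at each listed time point. If a change is still to be reported, state whether it is relative or in percentage points. Define the reference reading in both arms, including usual care, where no turn is defined.
- Statistical Considerations: model the FiO2 level with starting FiO2 as a pre-specified covariate. Use the pre-move reading for short-term effects and the reading at randomisation for weekly comparisons between arms.
- Report how many readings started at 21%.

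The same bedside readings are used. The cost is a few sentences in the protocol and the data form, with no added infants, visits or measurements.
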